### 5.2 Rationale for Design

The pharmacokinetics and hepatic safety of EGCG with clomiphene citrate and letrozole are unknown. A 3-arm study will be conducted in women with and without fibroids to allow comparisons between these groups. The results of this study will be used to confirm hepatic safety for the larger multi-center FRIEND study. The pharmacokinetics and hepatic safety of EGCG with clomiphene citrate and letrozole are unknown. A 3-arm study will be conducted in women with and without fibroids to allow comparisons between these groups. The results of this study will be used to confirm hepatic safety for the larger multi-center FRIEND study.

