### 2.2 Patient Population

The population will consist of 36 women ages  $\geq 18$  to  $\leq 40$  years (at time of consent). Eighteen women will have intramural and/or subserosal fibroids and 18 women will be without intramural fibroids and/or subserosal fibroids. Participants will be recruited over approximately a 6-month period from the FRIEND Collaborative clinical sites (Johns Hopkins University, University of Illinois at Chicago, University of Chicago and Yale University).

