### 2.4 Treatment

The 36 women will be randomized to one of the following groups:

1. EGCG daily alone.
2. EGCG daily with clomiphene citrate 100mg for 5 days.
3. EGCG daily with letrozole 5mg for 5 days.

The purpose of studying EGCG in combination with clomiphene citrate or letrozole is to assess the safety of using them together prior to the initiation of the FRIEND study. It is expected that EGCG will decrease fibroid size and decrease humoral activity leading to improved quality of endometrium for implantation. Clomiphene citrate and letrozole are being used for ovulation stimulation as treatment for unexplained infertility. In view of the possibility of interaction and change in toxicity when both are used together for FRIEND study, it was suggested by our pharmacology reviewer to include EGCG with the addition of clomiphene citrate and letrozole for the safety study.

The initial screening visit will include EGCG levels, liver function, folate and estrogen levels. A genetics sample collection, urine pregnancy test and pelvic ultrasound will also be performed after informed consent. Patient will be given the EGCG (Green Tea extract) to start after the screening visit. Patients will be counseled on dietary restrictions while on EGCG.

Visit 1 will occur on menstrual cycle day  $3 \pm 2$  days. EGCG levels over 8 hours, liver function, and urine pregnancy testing will occur at this visit. Patients will be assigned into their groups and provided with their respective treatments at this visit.

Patient will return between days 8-10 of the cycle for Visit 2. EGCG levels over 8 hours, liver function, estrogen, and urine pregnancy testing will occur at this visit.

The patient will return for Visit 3 between days 14-16 for a pelvic ultrasound evaluation of endometrial thickness and ovarian characteristics.

The final study visit (Visit 4) will be approximately 4 weeks after initiation of the study treatment and will involve EGCG levels, liver function, folate, and urine pregnancy test and pill counts.

The 4 lab panels (screening, Visits 1, 2, and 4) will include EGCG and metabolite analyses, liver panel (AST, ALT, total bilirubin, ALP) and estrogen levels, and a urine pregnancy test. The EGCG analyses at visits 1 and 2 will include testing over 8 hours.

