## **2.7 Statistical Analysis**

Since the number of patients for this study is minimal and multiple factors are of concern, descriptive statistics will be used, and the study is expected to be under powered to perform any formal statistical inference. The number, mean, standard deviation, median, interquartile range of the level of the pharmacokinetic parameters of EGCG and 2 of the major metabolites at different time points and the difference from screening to Visit 1, Visit 2 or Visit 4, and the changes in liver function, estrogen levels, endometrial thickness, and follicular measurements will be presented for the three treatment groups, and then stratified by age group and/or the presence or absence of uterine fibroid. For comparison, a two-way ANOVA will be used to compare the effects of the three treatments and the presence of fibroids on the above outcome parameters. With a sample size of 36 patients for the three treatment groups, which includes 18 subjects with uterine fibroids and 18 without uterine fibroids, with an alpha of 0.05, the power of the study would be 0.44 and 0.85 for a medium (0.25) or large (0.4) effect size, respectively. There are insufficient preliminary data

in the literature to support or not support the reasonableness of these effect sizes. For the comparison of serum folate levels among wildtype MTHFR, MTHFR (C677T), and MTHFR (A1298C) patients, ANOVA (unadjusted) and multivariate linear regression will be used.

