#### 4.3.2 Study Population

Thirty-six (36) patients will be equally randomized via computer-generated randomization schedule to receive:

1. Two capsules of decaffeinated Green Tea extract (close to 800mg EGCG) taken orally on a daily basis for up to 2 months
2. Two capsules of decaffeinated Green Tea extract taken orally on a daily basis for up to 2 months with clomiphene citrate 100mg for 5 days
3. Two capsules of decaffeinated Green Tea extract taken orally on a daily basis for up to 2 months with letrozole 5mg for 5 days.

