#### 4.4.2 Possible risks/discomforts

Blood draws: Discomfort, bruising, infection or bleeding at the needle puncture site

Pelvic ultrasound: abdominal or pelvic discomfort

EGCG: Gastrointestinal upset; rare liver toxicity. The literature supports a potential relationship between high-dose Green Tea extract consumption and transient changes in serum liver enzymes. Rare ( $<5\%$ ) and transient liver transaminase elevations have been documented. Hepatotoxicity tended to show a temporal relationship between Green Tea extract consumption and effect onset with Green Tea extract-induced toxicity mainly manifesting after roughly 3-4 months of consumption. Daily intake of 1315 mg of Green Tea catechins containing 843 mg EGCG poses mainly mild, transient hepatic adverse effects. The incidence and severity of hepatotoxicity increased when Green Tea extract or EGCG was administered under fasted conditions, while exposure to Green Tea under fed conditions appears to alleviate such risk.

Clomiphene Citrate: Visual changes (such as blurring of vision, double vision, floaters), abdominal pain, nausea, vomiting, constipation, mood changes, headache, hot flashes, fatigue, abnormal endometrial thickening, multiple pregnancies, formation of ovarian cyst, breast discomfort, abnormal uterine bleeding, and bloating

Letrozole: Fatigue, dizziness, nausea, hot flashes, arthritis pain in your joints, back pain, increased cholesterol levels, formation of ovarian cysts, multiple pregnancies

Other risks: There is also the risk of loss of confidentiality. Filling out the questionnaires may make the subjects uncomfortable or feel some anxiety. There is a risk that information about the subject may become known to people outside of this study.

As this is a NIH (NICHD) funded study, your study information is protected by a Certificate of Confidentiality. This Certificate allows us, in some cases, to refuse to give out your information even if requested using legal means.

It does not protect information that we have to report by law, such as child abuse or some infectious diseases. The Certificate does not prevent us from disclosing your information if we learn of possible harm to yourself or others, or if you need medical help.

Disclosures that you consent to in this document are not protected. This includes putting research data in the medical record or sharing research data for this study or future research. Disclosures that you make yourself are also not protected.

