## 5.5 Randomization/Treatment Initiation

Thirty-six (36) patients will be equally randomized via computer-generated randomization schedule to receive: 1) 800 mg of decaffeinated EGCG taken orally on a daily basis with food for up to 2 months; 2) 800 mg of decaffeinated EGCG taken orally on a daily basis with food for up to 2 months with clomiphene citrate 100mg for 5 days; 3) 800 mg of decaffeinated EGCG taken orally on a daily basis with food for up to 2 months with letrozole 5mg for 5 days.

Treatment assignments will be randomized for age groups and presence of fibroids by a varying-block-size design. The DCC statisticians will generate the randomization scheme for the study.

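### The design cannot support using the results to confirm hepatic safety for the larger FRIEND study

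*Combined protocol and SAP*

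**What the plan says.** Section 5.2 states the intended use of the trial: "The results of this study will be used to confirm hepatic safety for the larger multi-center FRIEND study". Section 3.1 says the same and presents the analysis as a precondition for the larger trial. Hepatic safety also appears in the objective (2.1), the primary aim (4.1) and the design description (5.1).

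The statistical sections give liver safety a lesser role. Between-group change in liver function is a secondary outcome (2.6, 6.3), with no acceptable rate, margin, precision target or success criterion. Section 2.7 says that "the study is expected to be under powered to perform any formal statistical inference", and 6.4 repeats it.

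On size, section 5.5 says "Thirty-six (36) patients will be equally randomized via computer-generated randomization schedule to receive" one of three regimens. On exposure, section 4.3.2 has the extract "taken orally on a daily basis for up to 2 months" in every arm, and section 2.4 places the final visit "approximately 4 weeks after initiation of the study treatment". On timing of harm, section 4.4.2 describes "Green Tea extract-induced toxicity mainly manifesting after roughly 3-4 months of consumption". It also calls transient transaminase elevations rare, at under 5%.

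**The concern.** The rationale promises a conclusion for which the analysis plan supplies no test, no criterion and no precision. Calling the analysis descriptive in 2.7 does not withdraw the use announced in 3.1 and 5.2, so the two parts of the protocol disagree about what the result is for.

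The stake is the decision that follows. If no woman has a liver event, the protocol as worded allows hepatic safety to be declared confirmed for a larger trial. The data would still be compatible with event rates above the only background figure the protocol gives, and women would not have been observed in the period when it says toxicity mainly appears. The gap is widest for EGCG with clomiphene or letrozole, which 3.1 and 5.2 name as unknown and which rests on 12 women per combination.

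**Working it through.** **The plan's own figure.** The documents give no sample size or precision calculation for hepatic safety. The only stated operating characteristic is the power of the two-way ANOVA in 2.7 and 6.4: 0.44 and 0.85 at effect sizes 0.25 and 0.4, N = 36, alpha 0.05. Taking the noncentral F with noncentrality N × f² (36 × 0.0625 = 2.25 and 36 × 0.16 = 5.76) and 2 and 30 degrees of freedom, the treatment effect has power 0.23 and 0.52, so the stated values are not reproduced. That is a separate matter; nothing below depends on it.

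**Inputs.** N = 36 (2.2, 5.5); equal allocation to three arms, so 36 / 3 = 12 per arm and 24 on a combination; exposure up to 2 months (4.3.2, 5.5); onset mainly after roughly 3-4 months (4.4.2).

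**Best case: no liver event.** The exact upper bound with zero events in n women is 1 − 0.05^(1/n) one-sided, and 1 − 0.025^(1/n) as the upper limit of a two-sided 95% interval.

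| Group | n | One-sided 95% | Two-sided 95% |
|---|---|---|---|
| All women | 36 | 8.0% | 9.7% |
| Both combination arms pooled | 24 | 11.7% | 14.2% |
| One arm | 12 | 22.1% | 26.5% |

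One event in 36 raises the overall bounds to 12.5% and 14.5%. No dropout rate is stated. If 30 of 36 women were evaluable (an assumption, close to the 33 of 39 completers in the EGCG trial described in 3.3), zero events would leave 9.5% and 11.6%.

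**Chance of seeing no case**, (1 − p)^n:

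- p = 5%: 0.95^36 = 0.158 in all women; 0.95^12 = 0.540 in one arm.
- p = 2%: 0.98^36 = 0.483 in all women; 0.98^12 = 0.785 in one arm.

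**Scale.** Excluding 5% with zero events takes ln 0.05 / ln 0.95 = 58.4, so 59 women one-sided, or ln 0.025 / ln 0.95 = 71.9, so 72 two-sided. This shows the distance between the design and the claim; it is not a proposal to enlarge the trial.

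**Stopping rule.** Section 4.3.6 ends the trial at three or more cases of active liver disease, and 3 / 36 = 8.3%. By the binomial tail, the chance of reaching three cases in 36 is 0.27 at a true rate of 5%, 0.56 at 8% and 0.71 at 10%. Not reaching it is weak evidence of a low rate.

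**Exposure against onset.** The stated maximum of 2 months ends before 3 months. The visit narrative (4.3.3) puts the last visit at day 30-35, while the column headings of the schedule in 5.9 run to day 64-70. The table may have been distorted in extraction, and the two timings should be reconciled. Even 70 days, counted from the start of the study, is about 2.3 months.

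**The case against.** The strongest reply is that the disputed word sits in one rationale sentence (printed once in 3.1 and twice in 5.2), while the operative text is modest. The primary aim is to assess, liver function is secondary, no confirmatory test is set, and the lack of power is disclosed. This stands to the extent that nobody should infer a planned formal safety test; there is none. But the stated use of the result remains, and the disclosure contradicts it rather than qualifying it.

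Second, participants are protected by individual termination, DSMB review of liver toxicity and the three-case rule, and continuous changes in liver tests are analysed as well. These are real safeguards during the trial. They are not a criterion for concluding that the regimen is safe.

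Third, the visit schedule suits an early-interaction question: liver tests on EGCG before the 5-day drug, several days after it, and at the final visit. For EGCG alone, 3.3 cites a 4-month trial at 800 mg with no adverse effects observed. Both points are fair. However, that trial reports 22 treated women, so zero events leaves a one-sided bound of 1 − 0.05^(1/22) = 12.7%, and as described it gives no data on the combinations.

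Some stronger readings are tempting and should be resisted:

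- A reader might infer that the trial cannot exclude a 10% rate. With all 36 women evaluable and no event, it does, since 0.9^36 = 0.023.
- A reader might infer that the design would miss a clinically relevant rate. At a true 5%, the chance of at least one case in 36 is 84%; the 54% chance of none applies to a single arm. The documents also define no clinically relevant rate, and their figure of under 5% refers to transient transaminase elevations, not to the 4.3.6 criteria.
- A reader might infer that no toxicity can appear within 2 months. Section 4.4.2 says mainly, so earlier events remain possible.

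**Conclusion.** The concern holds. The announced use of the results requires a property the design lacks: with a spotless outcome, rates up to 8.0% (one-sided) or 9.7% (two-sided) overall, and 22.1% or 26.5% in each arm, remain compatible with the data, and no criterion says what rate would count as safe.

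The precision argument needs only the sample size, equal allocation and independent women with complete follow-up; any dropout widens the bounds. The exposure argument is conditional. It is tempting to conclude that 2 months is too short for FRIEND, but FRIEND's treatment duration is not in these documents, so the mismatch matters for FRIEND only on the assumption that its treatment exceeds 2 months. What the documents do establish is that the period in which they place most toxicity is not observed here.

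**What to change.** 1. In 3.1 and 5.2, replace the claim to confirm hepatic safety with: *provide preliminary hepatic tolerability data for up to 2 months of exposure*. Add that the 3-4 month onset period is not observed.
2. In 2.7 and 6.4, add a table of the proportion of women meeting those 4.3.6 liver thresholds that the scheduled tests can measure (ALT, AST, total bilirubin). INR and eosinophils are not in the panel listed in 2.4 and Table 1, so the INR, symptom and eosinophil components should be reported only where collected, with the number assessed.
3. Give exact 95% confidence intervals overall and per arm, and state the upper bounds in the trial's conclusion.

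The cost is protocol wording, one more table and a less favourable conclusion. No change to sample size, dose or any clinical rule is proposed.

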### 5.3 Recruitment

#### *Hospital/Local Health Care Referrals*

Subjects will be recruited at each site from individual practice(s) as well as faculty/resident clinics.

#### *Local Advertisements*

Advertisements will be placed in local newspapers and will be continued on a regular basis if response is good.

#### *IRB Approval*

It is expressly acknowledged that all informational material that could be construed to be advertising will be approved by the appropriate IRB prior to dissemination.

### 5.4 Informed Consent

Once subjects have been identified, they will be referred to the site clinical coordinator or his/her designee. The clinical protocol will be explained to potential subjects by the physician investigator or the coordinator depending on the clinical circumstances. Inclusion and exclusion criteria will be reviewed. After the study has been completely explained, they will be given the informed consent documents to review. Some individuals may wish to complete the informed consent process at the time of this discussion. In these cases, the informed consent documents will be signed once all questions are resolved. In other cases, the subjects may wish to take the consent forms home for further consideration. In these cases, the coordinator will set up a tentative timeframe to be back in touch with the subjects. The consents can be signed either with the coordinator or with a physician once all questions have been answered to the satisfaction of the potential patient. A signed informed consent document, approved by the IRB at the study site, will be confirmed on all subjects prior to the baseline evaluation. In order to be eligible for enrollment and randomization, all inclusion and exclusion criteria must be met.

## 5.5 Randomization/Treatment Initiation

Thirty-six (36) patients will be equally randomized via computer-generated randomization schedule to receive: 1) 800 mg of decaffeinated EGCG taken orally on a daily basis with food for up to 2 months; 2) 800 mg of decaffeinated EGCG taken orally on a daily basis with food for up to 2 months with clomiphene citrate 100mg for 5 days; 3) 800 mg of decaffeinated EGCG taken orally on a daily basis with food for up to 2 months with letrozole 5mg for 5 days.

Treatment assignments will be randomized for age groups and presence of fibroids by a varying-block-size design. The DCC statisticians will generate the randomization scheme for the study.

## 5.6 Physical Exam

A physical exam with standard pelvic and breast exam will be performed on all patients by a study physician. Height, weight and waist and hip circumferences will be recorded to the nearest 0.1 cm, 0.1 kg and 1 cm, respectively. Waist will be measured at the level of the umbilicus and hip circumference will be measured at the widest diameter. Participants will be weighed while dressed in light clothing, without shoes. Weight will be collected at each cycle initiation visit; however, height, waist and hip circumferences are only collected at the screening and end of study drug visits. Blood pressure will be determined in the right arm in the sitting position. Large cuff will be used as necessary. Blood pressure will be assessed at each visit. Elevated blood pressures ( $\geq 160/100$ ) will be repeated following acclimation to the study environment. All patients aged 21 and older should have had a normal Pap smear in accordance with current ACOG guidelines. If not, one should be performed at the screening exam. Patients with cytological abnormalities will need to have these resolved prior to study entry.

## 5.7 Transvaginal Ultrasound Exam

An ultrasound exam will be performed with a transvaginal probe. For subjects who cannot tolerate a transvaginal probe, a transabdominal ultrasound evaluation will be performed. The following measures will be obtained at screening: uterine dimensions, leiomyoma presence and size, other uterine abnormalities, endometrial thickness, ovarian size in three dimensions, the size of the largest ovarian follicle, follicle count in the largest plane and ovarian morphology. Ovarian size is determined by measuring the largest plane of the ovary in two dimensions and then turning the vaginal probe 90 degrees and obtaining a third measurement. Endometrial thickness is the largest anterior-posterior measurement of the endometrium in the sagittal plane. Ovarian volume is determined by the formula for a prolate ellipsoid (length x width x height x  $\pi/6$ )(Pache, Hop et al. 1991). If the patient has had no prior test of tubal patency, this may be the desired time to perform a sonohysterogram to determine tubal patency. Only endometrial thickness and ovarian follicular measurements will be measured at visit 2.

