### 3 Background and Significance

#### 3.1 Overview

Uterine leiomyomas (fibroids) affect 30-50% of reproductive-age women and are a significant cause of infertility. Intramural and submucosal fibroids reduce the likelihood of pregnancy (RR=0.3-0.7) compared to unaffected women. Surgical removal of fibroids can restore fertility; however, recurrence rates are high, and benefits are often temporary. Importantly, serious postoperative consequences such as adhesions can adversely affect a woman's fertility and health in general. Hormonal therapies that induce medical menopause can be used to reduce fibroid size, but these therapies also prevent pregnancy. There is a critical need for effective, non-hormonal, non-surgical fertility treatment options for women with fibroids that may distort the uterine cavity. Our long-term goal is to develop novel non-hormonal treatments for uterine fibroids. Green Tea leaves contain polyphenols and catechins, such as epigallocatechin gallate (EGCG). Studies from our group and others have shown that EGCG is the most abundant and active compound responsible for effects of Green Tea extracts. Notably, EGCG can be taken during pregnancy and there are no known teratogenic effects. EGCG polyphenols inhibit key pathways of tumor growth by modulating signaling pathways involved in cell proliferation, transformation, inflammation, apoptosis, metastasis and invasion. Prior to initiating a randomized, double-blind, multi-center, prospective, clinical trial of EGCG versus placebo in women with uterine fibroids to evaluate birth rate a pharmacokinetic and hepatic safety analysis must be conducted. The pharmacokinetics and hepatic safety of EGCG with clomiphene citrate and letrozole are unknown. A 3-arm study will be conducted in women with and without fibroids to allow comparisons between these groups. The results of this study will be used to confirm hepatic safety for the larger multi-center FRIEND study.

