### 4.3 Treatment Design, Study Population, and Study Summary

#### 4.3.1 Treatment Design

This will be a pharmacokinetic trial involving 36 healthy adult female subjects. There will be 18 subjects with uterine fibroids and 18 without uterine fibroids. The randomization scheme will be coordinated through the DCC and the randomization will be stratified for age groups 18-29 and 30-40 and presence of fibroids. The population will consist of 36 women with or without uterine fibroids, age  $\geq 18$  to  $\leq 40$  years (at time of consent).

The appropriate study candidates will be recruited from the clinics of the 4 FRIEND Collaborative sites after obtaining informed written consent from the female subjects. Recruited participants will meet the inclusion and exclusion criteria detailed below. Monitoring of this trial at all sites will be conducted by the Yale DCC.

[figure not shown]

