#### 4.3.3 Study Summary

Recruitment and Prescreening: see Section 5 descriptions following.

Screening visit (anytime in cycle 1):

1. Obtain informed, signed consent.
2. Complete medical/gynecological/menstrual history and physical exam of female study participant.
  - Vital signs, height, weight, hip and abdominal circumference, BMI
  - Pap smear if necessary per current ACOG time-frame guidelines
  - Standard pelvic and breast exam conducted by physician or within past 12 months
3. Perform radiological exams.
  - Pelvic ultrasound measuring uterine and ovarian characteristics or within past 3 months
4. Laboratory tests: EGCG and metabolites, liver function, folate, estrogen levels, genetics sample collection and urine pregnancy test.
5. Dispense Green Tea extract and educate on dietary restrictions while taking Green Tea extract and with the importance of taking food. All patients to start Green Tea extract at this visit.
6. Contraception education. Patients will be counseled to use non-hormonal double-barrier method: a male/female condom plus spermicidal agents, cervical cap, diaphragm or sponge.
7. Concomitant medication collection.

Visit 1 (Day 1-5):

Patient will be seen on menstrual cycle day  $3 \pm 2$  days for clomiphene citrate/letrozole initiation visit

1. Vital signs and weight.
2. Laboratory tests: EGCG levels over 8 hours (0.5,1,2,4,6,8), liver function, folate, estrogen level, and urine pregnancy testing.
3. Concomitant medication collection and pill counts of EGCG.
4. Randomization and dispensation of clomiphene citrate/letrozole.
5. Contraception education. Patients will be counseled to use non-hormonal double-barrier method: a male/female condom plus spermicidal agents, cervical cap, diaphragm or sponge.

Visit 2 (day 8-10):

Patient will return several days after final clomiphene citrate/letrozole administration

1. Vital signs and weight.
2. Laboratory tests: EGCG levels over 8 hours (0.5,1,2,4,6,8), liver function, folate, estrogen level and urine pregnancy testing.

3. Concomitant medication collection and pill counts of EGCG and clomiphene citrate or letrozole as appropriate.
4. Contraception education. Patients will be counseled to use non-hormonal double-barrier method: a male/female condom plus spermicidal agents, cervical cap, diaphragm or sponge.

Visit 3 (day 14-16):

1. Pelvic ultrasound via a transvaginal probe or transabdominal transducer evaluation of endometrial thickness and ovarian characteristics.

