Visit 4 (day 30-35):

Patient will return for final study visit.

1. Vital signs and weight, hip and abdominal circumference, BMI
2. Laboratory tests: EGCG and metabolites, liver function, estrogen level, folate, and urine pregnancy test.
3. Concomitant medication collection. Return unused medications and pill counts of EGCG.

Future Studies: One tube of blood will be collected at each visit to be stored for future analyses related to this study.

*4.3.4 Inclusion Criteria*

1. Healthy women  $\geq 18$  to  $\leq 40$  years of age with or without uterine fibroids
2. Must use a double-barrier method for contraception

*4.3.5 Exclusion Criteria*

1. Subjects using Green Tea/EGCG within 2 weeks prior to study enrollment. Matcha (Japanese green tea), maca powder, green tea beverages and all other forms of green tea require a 2-week wash-out. Patients with a detectable EGCG level at the screening visit will be excluded.
2. Known liver disease (defined as AST or ALT  $>2$  times normal, or total bilirubin  $>2.5$  mg/dL).
3. History of alcohol abuse (defined as  $>14$  drinks/week) or binge drinking of  $\geq 6$  drinks at one time).
4. Subject using hormonal contraceptives: 3-month wash-out is required for all oral or cyclic progestins, GnRH agonists/ antagonists, gonadotropins, injectable contraceptives, oral contraceptives, contraceptive implants and previous use of clomiphene and letrozole.
5. Subjects who are pregnant or breastfeeding
6. Known hypersensitivity to the study drugs
7. Any chronic disease

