### 4.4 Risk/Benefit Assessment

#### 4.4.1 Possible Benefits

No direct benefits to participants.

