## 5.9 Schedule of Evaluations

Study procedure	Cycle 1					Cycle 2				
	Screening	Visit 1 (Day 1 -5)	Visit 2 (Day 8 -10)	Visit 3 (Day 14-16)	Visit 4 (Day 30 - 35)	Visit 5 (Day 36-42)	Visit 6 (Day 43-49)	Visit 7 (Day 50-56)	Visit 8 (Day 57-63)	Visit 9 (Day 64-70)
Informed consent	X									
Inclusion/exclusion criteria	X									
Demographic information	X									
Medical history	X									
Concomitant medications	X	X	X						X	
Gynecological history	X									
Menstrual history	X									
Vital signs and weight	X	X	X						X	
Height	X									
Hip and abdominal circumference	X									X
Physical examination	X									
Pap smear	X*									
Pelvic and breast exam	X**									
Genetics sample, laboratory test	X									
Pelvic ultrasound	X †						X			
EGCG levels and metabolites, laboratory test	X	X	X						X	
Liver function, laboratory test	X	X	X						X	
Folate, laboratory test	X								X	
Estrogen levels, laboratory test	X	X	X							X
Contraceptive counseling	X	X	X							
Dispense EGCG	X									
Pill counts of EGCG		X	X						X	
Randomization and dispensation of clomiphene citrate or letrozole			X							

Pill counts of clomiphene citrate and letrozole			X		
Urine pregnancy test	X	X	X		X

\*If necessary per ACOG guidelines

\*\*if not done within past 12 months

† if not done within past 3 months

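### Section 5.7 allows a sonohysterogram for tubal patency at the screening scan, but nothing in the trial uses the result and neither the schedule nor the risk section covers the procedure

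*Combined protocol and SAP*

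**What the plan says.** Section 5.7 describes the ultrasound examination. It lists what is measured at screening: the uterus, any leiomyomas or other uterine abnormalities, endometrial thickness, and ovarian size, follicles and morphology. Tubal patency is not on that list. After explaining how these measurements are made, the section adds that if a woman has had no earlier test of tubal patency, "this may be the desired time to perform a sonohysterogram to determine tubal patency".

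The other descriptions of screening name an ordinary scan only:

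- Section 2.4: "A genetics sample collection, urine pregnancy test and pelvic ultrasound will also be performed after informed consent".
- Section 4.3.3, screening visit: "Pelvic ultrasound measuring uterine and ovarian characteristics or within past 3 months".
- Section 5.9 has one imaging row, for pelvic ultrasound. Its footnote requires the screening scan only "if not done within past 3 months".

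On the population and purpose, 4.3.1 states: "This will be a pharmacokinetic trial involving 36 healthy adult female subjects". Under the inclusion criteria (4.3.4) each woman "Must use a double-barrier method for contraception". Section 4.4.1 reads: "No direct benefits to participants". Section 3.1 explains that before the later "clinical trial of EGCG versus placebo in women with uterine fibroids to evaluate birth rate a pharmacokinetic and hepatic safety analysis must be conducted", so the fertility question belongs to that later trial.

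**The concern.** Tubal patency matters when the question is whether a woman can conceive. Here the participants must avoid conception, and the questions are EGCG exposure and liver safety. A test of patency therefore has no evident role, yet the text allowing it sits among the study procedures, where a site may reasonably act on it.

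What is at stake is participant burden and safety, on a small scale. A sonohysterogram is a further, intrauterine procedure beyond the pelvic scan. A healthy volunteer could undergo it under a protocol that gives no research reason for it and does not list its risks. No effect is claimed on the pharmacokinetic, hepatic or other outcomes, on adverse-event attribution, or on baseline endometrial thickness.

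**Working it through.** The plan gives no figure on this point, so there is nothing to reproduce or recompute. The check is to go through each place where tubal patency would appear if the trial used it, and each place where the procedure would appear if it were a planned part of the study.

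**Does anything use the result?**

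| Place | Content | Items | Naming tubal patency or sonohysterogram |
|---|---|---|---|
| Eligibility (4.3.4, 4.3.5) | 2 inclusion + 7 exclusion criteria | 2 + 7 = 9 | 0 |
| Stratification (2.3, 5.1) | age group; fibroids | 2 | 0 |
| Outcomes (2.5, 2.6) | 1 primary + 5 secondary | 1 + 5 = 6 | 0 |
| Analysis (2.7, 6.4) | treatment, fibroids, age group, MTHFR genotype | – | 0 |

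The only outcomes that come from ultrasound are endometrial thickness and ovarian characteristics. Neither requires knowing whether the tubes are open.

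**Is the procedure planned or covered elsewhere?**

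| Place | Content | Items | Naming the procedure |
|---|---|---|---|
| Screening description (2.4) | pelvic ultrasound | – | 0 |
| Visit lists (4.3.3) | pelvic ultrasound at screening and Visit 3 | – | 0 |
| Schedule (5.9) | one imaging row, pelvic ultrasound | 25 rows | 0 |
| Risks (4.4.2) | blood draws, pelvic ultrasound, EGCG, clomiphene, letrozole, other | 6 headings | 0 |

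The pelvic ultrasound risk line mentions only abdominal or pelvic discomfort. Both terms occur in 5.7 and nowhere else in the supplied text.

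**Which scan is meant?** The sentence does not name a visit. It follows the list of screening measures, and the one statement about a later scan comes after it. The screening scan is the natural reading.

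**How many women could be affected?** The upper limit is the number screened who have no prior tubal test and whose scan is not waived under the 3-month rule. The documents give neither number, and the wording is optional, so no estimate is possible and the true figure may be zero. The zero counts above all show the same absence. They are not a measure of harm.

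**The case against.** The strongest reply is that the sentence directs nobody to do anything. It remarks on convenient timing, assigns no responsibility and records no measurement. On that reading, its absence from the visit lists, the schedule and the risk section shows that a sonohysterogram is not a study procedure at all, perhaps only something a clinician might do as part of care. The documents do not rule this out. However, the sentence stands in the study-procedures text, does not describe the test as usual care, and gives tubal patency as its only purpose. If it is clinical care, it does not need to be in the protocol.

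A second objection is that the consent pages were removed before review, so participants may be told about the procedure there. That limit is real. What can be said is only that 4.4.2 does not list it.

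A third is that nothing measurable follows: the number affected may be zero and no result changes. That is accepted, and it is why the point carries little weight. A related remark is that 5.7 has another mismatch, placing the follow-up endometrial and follicular measurements at visit 2, whereas 2.4 and 4.3.3 place that scan at Visit 3. That is a separate matter. It neither weakens this point nor is cured by the same change.

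**Conclusion.** The concern holds. Section 5.7 permits a procedure that serves no criterion, stratum, outcome or analysis of this trial, is in no visit list or schedule row, and is not listed in the protocol's risk section.

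Its weight is low: a small participant-safety and consistency improvement worth making, with no bearing on power, error rates or the interpretation of results. The textual absence is certain. Whether any participant would undergo the procedure is not known.

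The conclusion rests on two readings: that the sentence refers to the screening scan, and that its place among the study procedures allows a site to act on it. It makes no claim about the consent form.

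**What to change.** Delete from 5.7 the single sentence about women with no prior test of tubal patency. The screening scan in 5.7 is then the pelvic ultrasound named in 2.4, 4.3.3 and 5.9, and the ultrasound risk in 4.4.2 corresponds to what is done. The cost is one deleted sentence: no planned data are lost and no other section has to change.

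If the sponsor prefers to keep a mention, 5.7 could state plainly that a sonohysterogram is not a study procedure, though deletion is simpler. Retaining it as a study procedure would require a stated purpose, a schedule row and risk text, and no objective in the plan supports that extra work.
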